1.1.4 Using brain networks to predict tDCS response

Evidence points toward the importance of brain network hubs—nodes that are connected to many other nodes by edges—in neurodegenerative disorders. Nodes with high hub centrality are critical participants in a wide range of network operations supporting cognitive functions (van den Heuvel & Sporns, 2013) and are disproportionately affected in neurological syndromes (Stam, 2014). The tendency for a node to be a hub can be distinguished from more general measures such as network density, the total number of connections in a network, and can be expressed as a hub score, which quantifies the centrality of a node in information processing in a network (van den Heuvel, 2010). Brain regions with especially high hub scores participate in many processing pathways within the brain. Across the spectrum of neurodegenerative disorders, it is suspected that as nodes in critical brain areas are progressively degraded by disease, this is associated with changes in the recruitment of remaining hub nodes (Stam, 2014). Early in the course of degenerative disease, as specific brain regions are selectively affected, it is believed that there is an *increase* in the connectivity of remaining hubs in those regions that partially compensates for lost nodes and helps to maintain performance (Stam, 2014). However, as worsening disease leads to greater node loss, these compensatory changes cannot keep pace with neurodegenerative deterioration, resulting in decreasing hub scores in affected regions (Buckner et al., 2009; Engels et al., 2015). Eventually, when degenerated regions are severely affected, hub scores decline dramatically as the few remaining nodes do not harbor sufficient connections to contribute to networks. In the case of PPA, residual language abilities would then depend on the activity of relatively spared language regions. In a preliminary analysis of 65 subjects with PPA we found that hub scores are indeed decreased in different language centers in PPA variants. Thus, the hub score could serve as a metric in PPA to describe how affected and spared regions impact network functions at different stages of disease. Brain network hubs could also be positively influenced by interventions that enhance their connectivity. We posit that changes in hub scores could also provide a framework for understanding the impact of tDCS on language networks in persons with PPA.

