2.1 Primary Objective

- To determine the efficacy of tDCS + mCILT in improving language performance in persons with PPA compared to sham tDCS + mCILT.

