3.1 General Design

This is a double-blind, sham-controlled, crossover study. Groups will be counterbalanced according to PPA subtype. All participants will undergo baseline language testing and neuroimaging prior to receiving 10 treatment sessions over 2 weeks (Monday-Friday) of either real or sham tDCS paired with mCILT. Immediate post-treatment, 6 week and 12 week follow-ups will be obtained. Participants will then crossover into the second portion of the study whereby they will receive the opposite treatment protocol (real or sham tDCS + mCILT) and an additional 24 week follow-up. Treatment must take place within 2 days to 4 weeks of baseline testing. The overall timeline for each subject's participation is indicated below in Figure 1.

Figure 1: Timeline for each subject

Enrollment	Baseline MRI	Baseline 1	Baseline 2	Treatment	Follow-up	Follow-up MRI	6 week Follow-up	12 week Follow-up	12 week Follow-up MRI	
SCREENING	VISIT 1**	VISIT 2*	VISIT 3*	Visit 4-13	VISIT 14*	VISIT 15**	VISIT 16*	VISIT 17*	VISIT 18**	
- Informed Consent - Screening Forms - Demographics Form	MRI	-CCRSA -WAB 1 -CILT 1 -NWRT -LTROG Oral -PPT Picture -NACC Word Reading -NACC Sentence Repetition	-WAB 2 -CILT 2 -PRT -DDK -LTROG Written -PPT Words -Story -NACC Sentence Reading	tDCS mCILT OR Sham tDCS mCILT	+	- WAB - CILT - NWRT - PRT - LTROG Oral & Written - PPT Picture & Words - NACC Word reading, Sentence Reading & Repetition - DDK - CCRSA - Story	MRI	- WAB - CILT - NWRT - PRT - LTROG Oral & Written - PPT Picture & Words - NACC Word reading, Sentence Reading & Repetition - DDK - CCRSA - Story	-CCRSA -WAB 1 -CILT 1 -NWRT -LTROG Oral -PPT Picture -NACC Word Reading -NACC Sentence Repetition	MRI
~ 1 hour	~ 1 hour	~ 3 hrs	~ 3 hrs	~ 1.5 hrs	~ 3 hrs	~ 1 hour	~ 3 hrs	~ 3 hrs	~ 1 hour	

CONFIDENTIAL

Crossover Baseline	Crossover Treatment	Crossover Follow-up	Crossover Follow-up MRI	Crossover 6 week Follow-up	Crossover 12 week Follow-up	Crossover 12 week Follow-up MRI	Crossover 24 week Follow-up
VISIT 19*	VISIT 20-29	VISIT 30*	VISIT 31**	VISIT 32*	VISIT 33*	VISIT 34**	Visit 35

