3.1.5 Allocation to Interventional Group

Participants will be semi-randomized using a predetermined list generated by excel. Since this is a crossover study, all participants will eventually receive real stimulation - only the order will differ. Half of our participants will receive real tDCS first, and the other half will receive sham tDCS first. All participants will participate in mCILT.

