8.4.3 Network Neuroscience measures of response to tDCS + CILT

We will first test for the hypothesized relationship between node loss and hub scores by expressing node loss as a quadratic term in a multiple regression using the gray matter thinning at each node in the language network to predict hub scores, covarying for subject age and disease onset, with an FDR-corrected threshold of 0.05. Then, we will use a data-driven machine learning approach—support vector regression—using multivariate hub scores (Fornito et al., 2015) throughout the brain to predict behavior. We will use a leave-one-out cross validation strategy to identify the combination of nonlinearly weighted variables that predict behavior. The value of the machine learning model will be evaluated in terms of percentage of variance explained relative to selecting a similarly sized set of random variables (neuroimaging features including region cortical thickness and individual white matter connections) in 10,000 permutations for both the traditional regression and support vector regression models. It will additionally be tested against network density—the total connectivity of the network—as a control condition. Then, to test whether strong hubs account for the greatest variance in the data, we will correlate the support vector regression weights with region hub scores post-hoc. A significant positive correlation would indicate that stronger hubs account for higher variance in behavioral scores.

We will then use multiple regression to assess stimulation condition as a predictive variable for each language network node. If the predictor illustrates that hub scores increase in the presence of active tDCS, we will test whether effects tend to be concentrated near the site of

CONFIDENTIAL

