stimulation using a permutation test in which we shuffle the assignment of significant nodes for each network statistic uniformly at random across the brain. If the number of nodes concentrated in the anterior perisylvian nodes encompassed by our area of stimulation is greater than 95% of permutations, it will establish that the effects of mCILT or tDCS + mCILT are local to this region. Moreover, it will allow us to examine whether the effects of stimulation on hub scores are observed in different PPA phenotypes that express pathology at the site of stimulation (as in our nPPA/lvPPA subject) or remote from the site of stimulation (as in our svPPA subjects). Finally, to test if patterns of hub scores across the brain distinguish pre-from post-treatment, we will train support-vector classifiers in a leave-one-out fashion to distinguish pre-and post-treatment conditions within each phenotype using all node hub scores. We will use permutation testing to examine the accuracy of the classifiers against 10,000 null permutations to examine the significance of our results. Further exploratory analyses will examine the specific effect of mCILT alone on language network properties.

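### The locality test in Section 8.4.3 compares real with sham tDCS, so it cannot show that an effect of mCILT, or of the whole package, is local

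*Combined protocol and SAP*

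**What the plan says.** Section 8.4.3 of the combined protocol and SAP sets out a chain of hub-score analyses. The nodes of interest come from a regression: "We will then use multiple regression to assess stimulation condition as a predictive variable for each language network node". The locality test is conditional on that result: "If the predictor illustrates that hub scores increase in the presence of active tDCS, we will test whether effects tend to be concentrated" near the stimulation site. The significant nodes are then shuffled at random across the brain. If the observed count in the anterior perisylvian area exceeds the count in 95% of the shuffles, the section says "it will establish that the effects of mCILT or tDCS + mCILT are local to this region". It closes with a further plan: "Further exploratory analyses will examine the specific effect of mCILT alone on language network properties". No method, comparator or pair of scans is given for that last analysis.

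On what participants receive, Section 3.1.5 states: "All participants will participate in mCILT". Section 3.1 gives the other tDCS condition at crossover, again with mCILT. The primary objective in Section 2.1 has the same contrast: "To determine the efficacy of tDCS + mCILT in improving language performance in persons with PPA compared to sham tDCS + mCILT".

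On imaging, there is one MRI before treatment (Section 3.1.2), then scans immediately after treatment and at 12 weeks (Section 3.1.4). Under Section 6.4.6, Visits 18 and 19 serve as the crossover baseline. Visit 18 is the 12-week MRI, so the second-period baseline scan follows a course of mCILT.

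**The concern.** The decision rule draws a conclusion about something its test does not vary. The nodes entering the test are chosen because hub scores differ between real and sham stimulation. mCILT is the same on both sides of that comparison. The rule nevertheless names mCILT as one of the things whose effect would be shown to be local.

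If the rule is applied as written, a finding about tDCS could be reported as a regional brain effect of speech therapy, or of the combined treatment against nothing. The closing sentence of the section has a related gap. A specific effect of mCILT alone needs a condition without mCILT, and there is none.

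**Working it through.** The plan gives no figure to reproduce here. The question is which effects the design can identify.

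**Step 1: what the contrast contains.** For a node's hub score, let T be the change from baseline to follow-up common to both conditions for reasons other than mCILT (disease course, rescanning, the sham procedure). Let M be the effect of mCILT, and D the added effect of active over sham tDCS when given with mCILT.

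- Expected change under real tDCS + mCILT: T + M + D
- Expected change under sham tDCS + mCILT: T + M
- Difference: (T + M + D) − (T + M) = D

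The regression on stimulation condition targets D, so nodes selected by it carry information about where D occurs. The package against no treatment is M + D, which needs M.

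**Step 2: can M be obtained from any other part of the design?** The two sequences, two periods and two occasions (before and after treatment) give eight cells:

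| Sequence | Period | Post | tDCS | mCILT |
|---|---|---|---|---|
| Real first | 1 | 0 | 0 | 0 |
| Real first | 1 | 1 | 1 | 1 |
| Real first | 2 | 0 | 0 | 0 |
| Real first | 2 | 1 | 0 | 1 |
| Sham first | 1 | 0 | 0 | 0 |
| Sham first | 1 | 1 | 0 | 1 |
| Sham first | 2 | 0 | 0 | 0 |
| Sham first | 2 | 1 | 1 | 1 |

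The Post and mCILT columns are identical in every row. With intercept, sequence, period, post, tDCS and mCILT as the six columns:

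- Rank is 5 of 6. D is estimable, T and M are not separately estimable, and only T + M is.
- With change scores (intercept, sequence, period, tDCS, mCILT), mCILT equals 1 throughout and is aliased with the intercept. Rank is 4 of 5; D is estimable and M is not.
- Adding a hypothetical group scanned before and after an interval without mCILT raises the rank to 6 of 6, and M becomes estimable.

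This coding assumes no carry-over. Allowing for carry-over would add unknowns and would not free M.

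**Step 3: what the sham data can offer for mCILT alone.** They give T + M, which includes natural course and about 30 seconds of real current per sham session (Section 12.1). In real-first participants the sham period follows a full course of real tDCS. Crossover comes after the 12-week visit (Section 6.4.6), which is when Section 7.6 expects benefit to peak, and Section 1.1.2 reports pilot language gains lasting to 12 weeks. Residual real-tDCS effects in their sham period are therefore plausible on the protocol's own account.

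The sham data free of earlier real tDCS are period 1 of the sham-first half: 62 / 2 = 31 if enrolment is full. Section 8.3 plans for 25% attrition but gives no rate for period 1. If all of that loss fell before the first follow-up scan, 31 × 0.75 = 23.25 would remain. At the planned rate the number therefore lies between about 23 and 31.

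**The case against.** The protocol uses tDCS + mCILT as the name of the active condition, judged against sham tDCS + mCILT. On that reading, half of the quoted conclusion is loose wording for the correct contrast. The sentence that follows it in Section 8.4.3 speaks of effects of stimulation on hub scores, and Section 2.2 frames the network objective around tDCS. This stands as evidence of a wording slip rather than a plan to credit speech therapy. It does not rescue the mention of mCILT, which the sentence lists as a separate alternative.

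A reader might also infer several stronger things that the documents do not support:

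- **That the plan claims to establish an effect of mCILT alone.** It says only that exploratory analyses will examine it. The claim to establish something belongs to the locality sentence.
- **That the locality test is invalid.** Whether the added tDCS effect is local is a question this contrast can address. Only the attribution goes too far.
- **That the decision rule could pass off disease progression as a local therapy effect.** Change common to both conditions largely cancels in real versus sham, and treatment order is split in half (Section 3.1.5). The section does not say how the node regression handles period, so cancellation is not guaranteed, but nothing in the text shows a bias. Progression is mainly a problem for the exploratory pre-post analysis.
- **That untreated hub scores are known to move materially during follow-up.** Section 1.1.4 describes worsening disease "resulting in decreasing hub scores in affected regions" and presents an early compensatory rise as a belief. It concerns disease stage and gives no rate over the trial's weeks.

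Finally, the interval from the immediate to the 12-week scan contains no mCILT and has some bearing on drift. It follows exposure, however, so it mixes drift with fading treatment effects and does not isolate M.

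**Conclusion.** The concern holds for the attribution. As written, a positive locality test would be said to establish something about mCILT, or about the package against no treatment, that the real-versus-sham comparison cannot show. It can localise only the added effect of active over sham tDCS given with mCILT. This follows from the allocation and the stated predictor, and does not depend on sample size, power or effect size.

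The exploratory analysis of mCILT alone likewise has no mCILT-free comparator. It can describe change under sham tDCS + mCILT but cannot separate that from natural course. How large natural change would be is not given in the documents.

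The reach is limited to a secondary network analysis and an exploratory one. The primary WAB-AQ comparison of real with sham tDCS is not affected.

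**What to change.** Two wording changes in Section 8.4.3:

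1. Restate the conclusion of the locality test as: *the effect of active versus sham tDCS, given with mCILT, is local to this region*. Delete the reference to effects of mCILT.
2. Describe the closing exploratory analysis as *uncontrolled change from baseline under sham tDCS + mCILT*, and state that it cannot be separated from natural course. Report period 1 of the sham-first participants, who have had no earlier real tDCS, at least as a sensitivity analysis. Making that subset the only analysis is defensible but not required, because it gives up about half of the sham data. Using both periods with results shown by sequence is also reasonable.

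No new arm, visit or scan is needed. The cost is a weaker claim from the secondary and exploratory network analyses. A condition without mCILT would be needed only if the sponsor wants to claim an effect of mCILT itself.

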4.5 Total Number of Subjects and Sites

We intend to enroll up to 62 subjects: 31 naPPA/lvPPA; 31 svPPA

Subjects will be stimulated and tested in HUP or Perelman School of Medicine buildings. Depending on the availability of rooms, four testing sites may be employed: Neurology out-patient offices in the Perelman Center, Neurology out-patient offices on Ravdin 2, laboratory of [name] (Gibson 3), or laboratory of [name] (Goddard). The tDCS device is portable and no special equipment is required.

Additionally, if it is requested by the participant, we may conduct study sessions in the participant's home. In order to be eligible for home visits, patients must live within 40 miles, or approximately one hours, of the University of Pennsylvania. Ultimately, the discretion for eligibility of home visits will be up to the Principal Investigator, in order to best effectively and efficiently manage the lab's resources. If participants do qualify for home visits, they will be required to come to the lab for their first stimulation session. If the patient does not experience any adverse events during that stimulation session and if the other requirements are met, then all subsequent stimulation sessions would be conducted in the participant's home. Again, we would like to stress that this is only an option, not a requirement, which participants may choose if it is more convenient for them. Study visits not requiring the use of tDCS may be conducted at the participant's home if this situation proves to be more convenient for the participant.

4.6 Vulnerable Populations:

Children, fetuses, neonates, or prisoners are not included in this protocol.

Although not directly targeted, mentally disabled persons, economically or educationally disadvantaged persons, and/or employees or students of the University of Pennsylvania will not be denied enrollment and any special protections and/or additional safeguards will be undertaken

CONFIDENTIAL

in order to protect the rights and welfare of these subjects from coercion or undue influence as appropriate.

5 Study Intervention (Study drug, device, biologic, vaccine, food etc.)

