8.3 Sample Size and Power Determination

To calculate power, we started from an ambitious but realistic estimate of the population available at the participating recruitment sites. We intend to recruit 62 subjects, although 25 subjects will be adequate to detect a difference between real and sham stimulation within each group (alpha = 0.05; power = 0.8). Although our historical attrition rate has been 15%, we will conservatively anticipate a 25% attrition rate and will therefore enroll 31 subjects in each PPA variant arm.

CONFIDENTIAL

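### Section 8.4.3 asks whether stimulation affects hub scores in different PPA phenotypes but names no stimulation-by-variant test, and the outputs it does name cannot show a difference between variants

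*Combined protocol and SAP*

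**What the plan says.** Section 8.4.3 handles the effect of stimulation on the language network in three steps.

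- **Node regression.** "We will then use multiple regression to assess stimulation condition as a predictive variable for each language network node". Stimulation condition is the only predictor named.
- **Localisation.** If hub scores rise under active tDCS, the plan runs a "permutation test in which we shuffle the assignment of significant nodes for each network statistic uniformly at random across the brain" and asks whether the significant nodes concentrate around the stimulated anterior perisylvian area. It then says that "it will allow us to examine whether the effects of stimulation on hub scores are observed in different PPA phenotypes", contrasting variants with pathology at the site (naPPA/lvPPA) and remote from it (svPPA).
- **Classifiers.** Support-vector classifiers are trained to "distinguish pre-and post-treatment conditions within each phenotype using all node hub scores".

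Variant does not enter a hub-score model as a modifier of stimulation anywhere else. The mixed model in 8.4.1 concerns language performance in each variant group; its listed fixed effects are sequence, period, treatment and treatment-by-period. In 8.4.2 variant is a candidate predictor of WAB-AQ responder status, not of hub-score change.

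On numbers, section 4.5 states: "We intend to enroll up to 62 subjects: 31 naPPA/lvPPA; 31 svPPA". Section 8.3 states that "25 subjects will be adequate to detect a difference between real and sham stimulation within each group (alpha = 0.05; power = 0.8").

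**The concern.** Whether stimulation acts differently when the pathology lies under the electrode or away from it is a question about a difference between two groups of people. It needs an estimate of that difference and its uncertainty. None of the three steps gives one:

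- the node regression, as described, gives an effect of stimulation;
- the permutation test asks where in the brain significant nodes fall;
- the classifiers separate pre- from post-treatment inside one phenotype at a time, which is neither the real-versus-sham contrast nor a comparison between phenotypes.

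An analyst following this text would have, at most, a map of significant nodes for each variant. The easy next step is to report a difference where one map shows effects and the other does not. That step is invalid: a significant result in one group and a non-significant result in the other is not evidence that the two effects differ. What is at stake is a mechanistic claim about phenotype whose error rate no threshold in the plan controls.

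**Working it through.** **Inputs**

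- 25 subjects per variant group, alpha 0.05, power 0.80 (8.3). Two-sided testing is assumed, because the plan does not say.
- 31 enrolled per variant (4.5, 8.3) and 25% attrition (8.3).
- No effect size or SD is given, and no power for hub scores. Using the 8.3 power here is an assumption, so a range is shown.

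**The plan's own figures.** The 25 per group cannot be reproduced without an effect size. Solving backwards with a paired two-sided t-test, 25 subjects at 80% power correspond to a within-subject standardised difference of 0.584 SD. Enrolment of 31 matches 25 × 1.25 = 31.25. Dividing by the retained share instead gives 25 / 0.75 = 33.3, so 34. With 31 enrolled and 25% lost, 31 × 0.75 = 23.25, or about 23 completers.

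**How often equal effects look different.** Take one test per variant, independent groups and the same true effect in both. If each test has power p, the chance that exactly one is significant is 2p(1 − p).

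| Power p | Where it comes from | 2p(1 − p) |
|---|---|---|
| 0.90 | assumed | 2 × 0.90 × 0.10 = 18% |
| 0.882 | 0.584 SD, all 31 complete | 2 × 0.882 × 0.118 = 21% |
| 0.80 | 0.584 SD, 25 complete | 2 × 0.80 × 0.20 = 32% |
| 0.763 | 0.584 SD, 23 complete | 2 × 0.763 × 0.237 = 36% |
| 0.70 | assumed | 2 × 0.70 × 0.30 = 42% |
| 0.50 | assumed | 2 × 0.50 × 0.50 = 50% (maximum) |
| 0.30 | assumed | 2 × 0.30 × 0.70 = 42% |

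A simulation of 200,000 trials with 25 per variant and 0.584 SD in both gave 31.9% for exactly one significant. A direct test of the between-variant difference was significant in 5.0% of the same trials.

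**What the direct test can detect.** Suppose the effect is 0.584 SD in one variant and zero in the other, with 25 in each. Comparing the within-subject differences between variants by a two-sample t-test, the noncentrality is 0.584 × √(25/2) = 2.065 on 48 degrees of freedom, and power is about 53%. With 23 per variant it is about 49%.

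**The case against.** The strongest reply is that the invalid decision rule is not in the text. A reader might infer that the plan commits to running the regression separately by variant and declaring a difference when only one is significant. The documents do not support that. They say only that it will be examined whether effects are observed in the phenotypes, which can also be read as asking whether effects occur in each one. Likewise, the regression is described as multiple and no full list of terms is given, so the absence of variant is silence, not a stated exclusion. Both points stand. What remains is that the section poses an at-site versus remote contrast and names no output that could answer it.

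A reader might also take this contrast for one of the trial's main inferences. Section 2.2 mentions variants only for baseline hub characteristics and aphasia severity, and the phenotype remark in 8.4.3 follows a step that is itself conditional on hub scores rising under active tDCS.

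Finally, the percentages might be read as error rates of this analysis. They are not. The 80% power in 8.3 names no endpoint, the 0.584 SD is back-solved, and the formula covers one test per variant, whereas the plan has many nodes and a spatial test. The figures show the size of the problem for a single pair of tests and no more.

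**Conclusion.** The concern holds as a gap in method. Section 8.4.3 raises a between-variant question about stimulation and hub scores, specifies no stimulation-by-variant term or contrast, and relies on outputs that cannot show that the effect differs by variant. Inferring a difference from significance in one variant only would be invalid. For a single pair of tests with equal true effects it would mislead in about a fifth of trials at 88% to 90% power, about a third at 76% to 80%, and half at 50%, against 5% for one interaction test. These figures assume independent groups and borrowed or assumed power; multiple nodes and FDR control would change them.

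This is worth correcting before the data are seen, but it concerns a secondary mechanistic analysis. The primary WAB-AQ comparison is unaffected.

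**What to change.** In 8.4.3, specify one hub-score model per node, or for a prespecified perisylvian summary, fitted in all participants. Include stimulation, variant and stimulation-by-variant, together with period, sequence and a subject random effect in line with 8.4.1. Apply FDR control to the interaction across nodes. State that a phenotype difference will be claimed only from the interaction, reported as a difference in effect with a 95% interval, and that per-variant effects will be given as estimates with intervals.

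The cost is SAP wording and a little more analysis; no new data, visits or participants are needed. The drawback is limited power: about 53% in the favourable case worked above (full effect in one variant, none in the other, 25 in each) before any multiplicity control. The section should therefore also say that a non-significant interaction will not be read as equal effects.

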3.1.4 Follow up Phase

There will be an immediate, 6-week and 12-week follow-up following both the initial component. The crossover component will have an additional 24 week follow-up. The full language assessment will be repeated at each follow-up. Subjects will also be asked to complete an MRI scan at the immediate and 12 week follow-ups. Depending on the patients stamina, language assessments may take three visits.

The follow-up visit may be conducted via tele-assessment.

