6.4.6 Visits 19-35 (Crossover)

Participants will crossover into the second half of the study after the 12 week follow-up. Visits 18 & 19 will serve as Baseline and then all study procedures will exactly match the first half of the study. The crossover will include an additional follow-up visit at 24 weeks.

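### Section 8.4.3 does not keep each person's repeated scans together in the folds or shuffles of the pre/post classifier; if they are split, the test is far too conservative

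*Combined protocol and SAP*

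**What the plan says.** Section 8.4.3 describes the analysis in two sentences: "we will train support-vector classifiers in a leave-one-out fashion to distinguish pre-and post-treatment conditions within each phenotype using all node hub scores", and "We will use permutation testing to examine the accuracy of the classifiers against 10,000 null permutations". Those sentences do not define the unit left out, the scaling of the scores or the shuffling rule.

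The scans are repeated measures. Section 3.1.4 says "Subjects will also be asked to complete an MRI scan at the immediate and 12 week follow-ups", and Figure 1 schedules MRI at Visits 1, 15, 18, 31 and 34, so a participant can have five. Section 6.4.6 adds: "Visits 18 & 19 will serve as Baseline and then all study procedures will exactly match the first half of the study". The Visit 18 MRI is therefore both the 12-week scan of period 1 and the baseline scan of period 2.

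For the language outcome, Section 8.4.1 handles repeated measures with a random intercept. Section 8.4.3 has no counterpart for the classifier.

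**The concern.** The question is whether a person's hub scores change. Stable differences between people are noise for that question, and pairing removes them.

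Suppose one scan is left out. The same person's other scan stays in the training set with the opposite label. The two scans resemble each other, so the classifier tends to give the left-out scan the wrong label. With no true change, accuracy then sits below 50%. A free shuffle often gives both scans of a person the same label, so the shuffled accuracies show little of this pull and stay close to 50%. The observed accuracy is compared with a reference that it cannot fairly reach.

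Free shuffling is the deeper problem. With no change, the pre and post labels are exchangeable within a person. They are not exchangeable across all scans, because the real labelling always gives each person one of each.

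A change in language-network properties is a secondary objective (Section 2.2), and this is the only multivariate test of a pre-to-post change in hub patterns. A null result from a test held below chance could not be interpreted. Settling folds and shuffles after seeing the data would leave an avoidable analyst choice.

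**Working it through.** **1. The plan's own figures.** Section 8.3 gives no sample size, power or accuracy target for the classifier, so there is none to reproduce. Its figures concern real versus sham: "25 subjects will be adequate to detect a difference between real and sham stimulation within each group (alpha = 0.05; power = 0.8" and "we will conservatively anticipate a 25% attrition rate and will therefore enroll 31 subjects in each PPA variant arm". No effect size is given. A two-sided paired t-test with 25 subjects and 80% power would imply a standardised within-person effect (dz) of about 0.58, which serves below as a reference shift. On enrolment, 25 / (1 − 0.25) = 33.3, or 34, whereas 25 × 1.25 = 31.25, or 31. At 25% attrition, 31 × 0.75 = 23.25, so about 23 complete per phenotype. The simulations use 23 or 25 pairs.

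**2. Model.** Each node has pre = u + e1 and post = u + e2 + shift, where u is the person's stable level. With between-scan correlation ρ and a shift of d standard deviations, dz = d / √(2(1 − ρ)). For d = 0.3:
- ρ = 0.5: 0.3 / √1.0 = 0.30
- ρ = 0.7: 0.3 / √0.6 = 0.39

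Assumed, not in the documents: 40, 100 or 300 nodes; ρ (scan reliability) from 0.4 to 0.9; share of nodes that shift; shift size; correlation between nodes from 0 to 0.2. Tests are one-sided permutation tests at 5%. The main runs use linear least-squares classifiers. Monte Carlo error is up to about 3.5 points in the runs behind setting A.

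**3. No true change, one scan left out, free shuffle.**
- 25 pairs, ρ 0.4-0.9: accuracy 5-33%, shuffled mean 49%, 0 rejections in 200 data sets in every scenario.
- 23 pairs, 40 or 100 nodes, ρ 0.5-0.7: accuracy 19-36%, shuffled mean 49-50%, no rejections.

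The actual size is about 0 instead of 5%.

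**4. Power for a small or local shift.** Setting A: 25 pairs, 100 nodes, 10% of nodes shifted by dz 0.58, ρ 0.4-0.9. Setting B: 23 pairs, 40 or 100 nodes, a quarter shifted by 0.3 SD, ρ 0.5-0.7.

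| Unit left out | Features | Shuffle | A | B |
|---|---|---|---|---|
| Scan | raw | free | 0-37% | 2-4% |
| Person | raw | free | 24-85% | 12-54% |
| Person | raw | within person | 61-87% | not tabulated |
| Scan | raw | within person | 91-96% | 31-96% |
| Person | differences | within person | 80-89% | 27-92% |

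In setting A the first row falls with reliability: 24-37% at ρ = 0.4, 8-14% at 0.6, 0.5% at 0.8 and 0% at 0.9. An ordinary linear support-vector classifier gave 22, 5, 3 and 0% (60 data sets, error up to about 6 points).

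**5. Which change matters most.** Keeping raw scores and scan-wise folds and changing only the shuffle gives, in setting B, 31% and 55% with 40 nodes and 68% and 96% with 100 nodes (ρ = 0.5 and 0.7). Differences, run alongside, gave 29, 53, 59 and 89%. The within-person shuffle accounts for most of the recovery.

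**6. Larger or wider shifts, scan left out, free shuffle.** The first three lines use setting A's 25 pairs and 100 nodes, at ρ = 0.4, 0.6, 0.8 and 0.9.
- 20% of nodes at dz 0.58: 88, 64, 16 and 0%, against 99.5% for differences.
- 50% of nodes at dz 0.58: 100, 100, 100 and 97%; with node correlation 0.2, 100, 99, 86 and 34%.
- 20% of nodes at dz 1.0: 99.5-100%.
- Setting B with a 0.5 SD shift: 29-90%.

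**The case against.** A reader might infer that the plan treats scans as independent cases and that the analysis therefore has almost no power. The documents support neither statement. Section 8.4.3 states no scan-wise folds, uncentred scores or free shuffling. Earlier in the same section leave-one-out is used to predict behaviour, where the natural unit is the subject, and the authors may intend the same here. Step 6 shows that even the worst reading runs from 0% to 100% power, depending on inputs the documents do not give.

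It can also be said that raw features are not the main cause, since within-person swapping alone restores power; that the error is conservative and produces no spurious claim; that hub change is also tested by the node-level regression on stimulation condition; and that no power is claimed for this analysis.

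All of this stands, and it limits the point to an unspecified method with a serious consequence under one ordinary reading. It does not remove the point. Whole-person folds with a free shuffle are still conservative, so intending the subject as the unit does not settle the shuffling rule. Conservatism is also a real cost where a null result would be read as no network change.

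**Conclusion.** The point holds as a gap in Section 8.4.3: nothing there keeps a participant's scans together in the folds or the permutations. Under scan-wise folds and free shuffling, accuracy with no change is about 5-36% against a shuffled mean near 49-50%, and the size is about 0. Power for a small or local shift can fall from roughly 30-90% to a few percent (setting B). In setting A it falls from 80-89% to between 0% and 37%, with the worst values where hub scores are most reliable. Large shifts would still be found, and widespread ones in most settings; correlated nodes with very reliable scores are an exception (34%).

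The below-chance mechanism appeared throughout the assumed range of reliability, but the power figures are illustrations under assumed inputs. The analysis is secondary and mechanistic, and the WAB-AQ comparison is untouched. The change should be made before the imaging data are analysed.

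**What to change.** In Section 8.4.3, replace the classifier and permutation sentences with wording such as:

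> Within each phenotype, classifiers will be trained on within-participant hub-score differences (post minus pre) or on person-centred hub scores. All scans of a participant will be left out together in each fold. The null distribution will be built from 10,000 random swaps of the pre and post labels within participant. For period 1 the pre scan is the Visit 1 MRI and for period 2 the Visit 18 MRI; the post scan is the [immediate / 12-week] MRI of the same period. Each treatment period is classified separately.

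The within-participant swap is the essential part. With 23 pairs there are 2^23 = 8,388,608 possible swaps, so 10,000 draws are feasible. Whole-person folds become necessary once scores are centred, because a person's two centred scans are mirror images and one would reveal the other. Differences or centring recover power that whole-person folds lose on raw scores (61-87% against 80-89% in setting A). The investigators must choose the post scan. Without a named pair, post minus pre is undefined, and pooling both periods could give the Visit 18 MRI both labels.

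The cost is this wording, a few lines of code, and the loss from this analysis of participants who lack one scan of the pair. No visit or scan is added.
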